3.3.2. Benefit Assessment

Generally, participants with non-dialysis dependent CKD undergo clinical assessment of anemia only every few months. This study may be beneficial to study participants by allowing participants access to anemia management and CKD care. Study participants will benefit from routine medical visits to the site and easy access to clinical facilities geared towards treatment of anemia in CKD. Study participants will also benefit from potentially obtaining a treatment for anemia in the form of an oral tablet which increases the ease of use for patients and health care providers. After administration of daprodustat, data suggest that the increases in Hgb are achieved with EPO exposure lower than those observed with rhEPOs. CCI

CCI - This section contained Clinical Outcome Assessment data collection questionnaires or indices, which are protected by third party copyright laws and therefore have been excluded.

3.3.3. Overall Benefit:Risk Conclusion

Daprodustat demonstrates a positive benefit vs. risk based on the evidence as follows. In clinical trials up to 24 weeks in duration in non-dialysis CKD participants, daprodustat treats Hgb to target range, with a safety profile consistent with the patient population. Furthermore, this protocol employs precautions to mitigate known and potential risks to randomized participants (Section 3.3.1). Given these precautions, as well as the potential benefit that daprodustat holds for the treatment of anemia associated with CKD compared to the current standard, the overall benefit risk balance is considered to be positive.

4. OBJECTIVES AND ENDPOINTS

Objectives	Endpoints
Primary	

 To compare the efficacy of daprodustat to placebo on mean change in Hgb levels 	
 Mean change in Hgb between baseline and the Evaluation Period (EP, mean over week 24 to week 28 inclusive)
Principal Secondary	

 To compare the proportion of participants achieving increases in Hgb when treated with daprodustat versus placebo. 	
 % of participants having a Hgb increase of ≥ 1.0 g/dL from baseline to EP.

 To compare daprodustat to placebo for health related quality-of-life 	
 Mean Change in SF-36 Vitality domain between baseline and Week 28
Safety	

 To compare the safety and tolerability of daprodustat to placebo 	
 Incidence and severity of AEs and serious adverse events (SAEs) including AEs of special interest and adjudicated MACE (composite of all-cause mortality, non-fatal MI and non-fatal stroke) Reasons for discontinuation of study treatment Absolute values and changes from

Objectives	Endpoints
	baseline in laboratory parameters, Blood Pressure (BP) and heart rate (HR)
Secondary	

 To compare daprodustat to placebo on additional Hgb endpoints 	
 N (%) responders, defined as mean Hgb within range. % time Hgb in range Mean change in Hgb from baseline.

 To compare daprodustat to placebo on the time to rescue 	
 Time to stopping study treatment due to meeting rescue criteria

 To compare daprodustat to placebo for improving symptoms of anemia of CKD 	
 Mean change from baseline by domain and overall symptom score on the Chronic Kidney Disease - Anemia Questionnaire (CKD-AQ) symptom questionnaire

 To compare daprodustat to placebo on the severity and change in symptoms 	
 Change from baseline in PGI-S

 To compare daprodustat to placebo for improving health related quality-of-life 	
 Mean Change in individual items of the SF-36 Vitality Domain from baseline. Mean Change in SF-36 Physical Function domain from baseline.

 To compare daprodustat to placebo on improving work productivity and regular daily activity impairment 	
 N (%) of patients currently employed on the WPAI-ANS-CPV Change from baseline in percent and mean hours work time missed on the WPAI-ANS-CPV Change from baseline in percent impaired (equivalent) on the WPAI-ANS-CPV Change from baseline in overall percent work impairment (equivalent) on the WPAI-ANS-CPV Change from baseline in percent activity impairment on the WPAI-ANS-CPV

 To compare daprodustat to placebo on improving health status 	
 Change in EQ-5D-5L utility score from baseline. Change in EQ-VAS score from baseline.

 To compare daprodustat to placebo on BP 	
 Change from baseline in SBP, DBP, and MAP at week 28 N (%) with at least one BP exacerbation event during the study

Objectives	Endpoints
Exploratory	

 Further evaluations to compare daprodustat to placebo on Hgb variability 	
 % of time Hgb is above or below range. Number (%) of participants with mean Hgb above and below range. Number (%) of participants with a Hgb < 7.5 g/dL Number (%) of participants with a > 2 g/dL increase in Hgb within any 4 week period up to EP N (%) of participants with a Hgb value \geq 13 g/dL during the treatment period Number of times Hgb \geq 13 g/dL during the treatment period % of time Hgb \geq 13 g/dL during the treatment period.

 Further evaluation to compare daprodustat to placebo on Hgb change. 	
 % of participants who achieved a Hgb increase of \geq 1.0g/dL % of time Hgb increase of \geq 1.0 g/dL from baseline % of participant having a Hgb increase of \geq 1.0 g/dL at each post-baseline visit. % of participants who achieved and maintained a Hgb increase of \geq 1.0g/dL between baseline and EP.

 To compare daprodustat to placebo on measures of iron status, rhEPO and Transfusion use 	
 Observed and change from baseline in hepcidin, ferritin, transferrin saturation, serum iron, total iron binding capacity (TIBC) Average monthly oral iron dose/participant (mg) to Week 28 N (%) of participants who reduced oral iron supplementation from baseline N (%) of participants requiring IV iron each month. Average monthly IV iron dose/participant (mg) to Week 28 Time to first IV iron, rhEPO and Transfusion use

Objectives	Endpoints
	
 Summary of frequency and dose of IV iron

 To compare daprodustat to placebo on renal function 	
 Estimated Glomerular Filtration Rate (eGFR) observed and change from baseline Serum creatinine observed and change from baseline N (%) transitioning to dialysis

 Evaluate the dose adjustment schemes 	
 Assigned dose by visit Most recent dose prior to Week 24, Week 28 and End of Treatment Maximum achieved dose Number (%) of participants with 0, 1, 2 or >2 dose adjustment Mean number of dose adjustments Time dose held for Hgb\geq13 g/dL

 To compare daprodustat to placebo on BP medication changes 	
 N (%) of subjects who had no change, an increase or a decrease in the number of BP medications from baseline to week 28 or final visit for non-completers

 To compare daprodustat to placebo on the severity and change in symptoms 	
 N(%) of participants within each PGI-C symptom change.

 To compare daprodustat to placebo for improving physical activity (actigraphy) 	
 Change in percent and mean number of hours of daily activity from baseline. Change in percent sleep efficiency from baseline.

5. STUDY DESIGN

5.1. Overall Design

This is a 28-week, randomized, double-blind, placebo-controlled, parallel-group, multi-center Phase 3 study in participants with anemia associated with chronic kidney disease (CKD) who are not on dialysis. This study will enroll anemic participants who have a HemoCue Hgb 8.5 to 10.0 g/dL, inclusive. These participants will have limited history of IV iron and be rhEPO naïve prior to screening and randomization.

This study includes a 4-week screening period, a 28-week treatment period, and a 4-week follow-up period ([Figure 1](#)).

[figure not shown]
The total duration of study participation for each participant will be approximately 36 weeks.

Participants will be randomized 1:1 to receive either daprodustat or matching placebo tablets. Participants will not be provided with the results of their HemoCue Hgb assessment during their participation in the study.

Daprodustat and placebo doses for participants will be titrated based upon HemoCue Hgb. Dose modifications for these participants will follow a protocol-specified dose adjustment algorithm to achieve and maintain Hgb within the target range of 11.0 to 12.0 g/dL, inclusive. Dose changes will be made programmatically in a blinded fashion by the IRT system in order to ensure that investigators and participants stay blinded to the study treatment and the dose adjustments.

A rescue algorithm is provided to minimize participants having an inadequate response to the treatment for their anemia for an extended period of time and to enable rescue therapy to be provided to the participants based on local clinical practice. (Section 7.7.2)

Figure 1 Study Schematic

5.2. Number of Participants

Approximately 1200 participants with anemia associated with CKD who are not on dialysis will be screened to achieve approximately 600 randomized and to target approximately 540 evaluable participants for an estimated total of 270 evaluable participants with a 1:1 randomization per study treatment group.

5.3. Participant and Study Completion

A participant is considered to have completed the study if he/she has completed all phases of the study including the Follow-up visit, which takes place 4 weeks after the end of study treatment.

The end of the study is defined as the date of the last visit of the last participant in the study or the last scheduled procedure shown in [Table 1](#) of Schedule of Activities (SoA).

5.4. Scientific Rationale for Study Design

This study has a 28-week Treatment Period ending with a 4-week evaluation period from Week 24 to Week 28. At the Day 1 visit the subjects will be randomized to the daprodustat or placebo arm by the IRT system and the study treatment will be administered in a blinded manner. From Day 1 to Week 24 participant study treatment dosage will be adjusted, per the dosing algorithm (Section 7.2), in a blinded fashion, by the IRT system.

A placebo control will enable assessment of the magnitude of the daprodustat response and comparisons for safety data. Additionally, a placebo comparator allows for an assessment of the extent to which any improvement in symptoms and HRQoL observed in the daprodustat treatment group is due to the drug's effect.

The risk of drop-outs due to lack of treatment effect is estimated to also be low in this patient population since, prior clinical studies have indicated that non-dialysis, CKD patients can maintain, or even increase, their current level of Hgb value without requiring frequent interventional therapy with rhEPOs or IV iron for anemia [Skali, 2013].

Participants eligible for this study will be naïve to rhEPO therapies and have limited IV iron exposure at the time of screening and randomization, but may be receiving oral iron which will be allowed to continue during the course of the study. Participants may start treatment or change their dose of iron (oral, or IV if intolerable to oral) to maintain their iron levels during the study. Participants who experience worsening of their anemia during the study may receive rescue therapy based upon the protocol defined rescue algorithm. Therefore, the use of a placebo arm in this study does not represent the absence of any treatment for anemia, but rather placebo in addition to appropriate standard of care.

5.5. Dose Justification

Daprodustat starting doses were selected to enable the majority of study participants to reach the target Hgb concentration after approximately one red blood cell (RBC) lifespan of treatment (almost 3 months, pharmacodynamic steady-state), without the need for any individual dose adjustments. However, due to the between-participant variability in Hgb response to a given dose of daprodustat and the relatively narrow Hgb target range, individual dose adjustments of daprodustat are still expected during the first few months of treatment.

The daprodustat starting doses and dose steps (including the highest dose level, 16 mg) were based on dose exposure-response longitudinal modeling of Hgb data collected across the Phase 2 program.

In this study, the starting dose of daprodustat will be 2 or 4 mg based on baseline Hemocue Hgb, or a matching placebo dose, for all participants. The starting dose is estimated to increase steady-state Hgb on average by approximately 1g/dL. This starting dose is consistent with the dosing algorithm being evaluated in the Phase 3 study [GlaxoSmithKline Document Number 2015N230102_03] for non-dialysis dependent participants who are not currently receiving rhEPO therapy.

6. STUDY POPULATION

Prospective approval of protocol deviations to recruitment and enrollment criteria, also known as protocol waivers or exemptions, is not permitted.

6.1. Inclusion Criteria

Participants will be eligible for inclusion in this study only if all of the following criteria apply at **screening (Week -4 and Week -2)** and **randomization (Day 1)**, unless otherwise specified:

Age

1. ≥ 18 years of age at the time of signing the informed consent.

Type of Participant and Disease Characteristics

2. **CKD:** Have CKD, confirmed at screening: Kidney Disease Outcomes Quality Initiative (KDOQI) CKD stages 3, 4, or 5 defined by Estimated glomerular filtration rate (eGFR) using the CKD Epidemiology Collaboration (CKD-EPI) formula [Levey, 2009].
3. **Hgb:** Stable HemoCue Hgb from 8.5 to 10.5 at screening visit (Week -4) and from 8.5 to 10.0 g/dL at randomization (Day 1) (Section 9.1).
4. **IV Iron:** Participants may receive up to one IV iron dose within the 8 weeks prior to screening and NO IV iron use between screening visit and randomization (Day 1).
5. **Oral Iron:** If needed, participant may be on stable maintenance oral iron supplementation. There should be $<50\%$ change in overall dose and no change in type of iron prescribed doses in the 4 weeks prior to Day 1 randomization visit.

Sex

6. Male and female participants are eligible. A female participant is eligible to participate if she is not pregnant (see Section 12.4), not breastfeeding, and at least one of the following conditions applies:
 - Not a woman of childbearing potential (WOCBP) as defined in Section 12.4 (Appendix 4), or
 - A WOCBP who agrees to follow the contraceptive guidance in Appendix 4 during the treatment period and for at least 4 weeks after the last dose of study treatment.

Informed Consent

7. Capable of giving signed informed consent as described in Section 12.2 Appendix 2 which includes compliance with the requirements and restrictions listed in the informed consent form (ICF) and in this protocol.

6.2. Exclusion Criteria

Participants will not be eligible for inclusion in this study if any of the following criteria apply at **screening (Week -4 and Week -2)** and **randomization (Day 1)**, unless otherwise specified:

CKD Related Criteria

1. **Dialysis:** On dialysis or clinical evidence of impending need to initiate dialysis within 180 days after randomization (Day 1).
2. **Kidney Transplant:** Planned living-related or living-unrelated kidney transplant within 28 weeks after randomization (Day 1).

Anemia-Related Criteria

3. **Transferrin saturation (TSAT)** <15% (Screening only)
4. **Ferritin** <50 ng/mL (Screening only)
5. **rhEPO or rhEPO analogues:** History of rhEPO or rhEPO analogue use within the 8 weeks prior to screening and rhEPO use between screening and randomization (Day 1).
6. **Transfusion:** History of transfusion within the 8 weeks prior to screening and transfusion between screening and randomization (Day 1).
7. **Aplasias:** History of bone marrow aplasia or pure red cell aplasia (PRCA)
8. **Other causes of anemia:** Megaloblastic anemia(untreated pernicious anemia and folate deficiency), thalassemia major, sickle cell disease or myelodysplastic syndrome
9. **Gastrointestinal (GI) bleeding:** Evidence of actively bleeding gastric, duodenal, or esophageal ulcer disease OR clinically significant GI bleeding \leq 8 weeks prior to screening through to randomization (Day 1)

Concomitant medication and other study treatment-related criteria

10. **Severe Allergic reaction:** History of severe allergic or anaphylactic reactions or hypersensitivity to excipients in the investigational product.
11. **Drugs and supplements:** Use of strong inhibitor of CYP2C8 (e.g., gemfibrozil) or strong inducers of CYP2C8 (e.g., rifampin/rifampicin).
12. **Ferric Citrate:** Ferric citrate use within 4 weeks prior to randomization (Day 1)

Prior Clinical Study Experience

13. **Other interventional study participation:** Use of other investigational agent or device prior to screening through to randomization (Day 1).
 - a. Note: at screening, this exclusion applies to use of the investigational agent within 30 days or within five half lives (whichever is longer).
14. **Prior treatment with daprodustat:** Any prior treatment with daprodustat for a treatment duration of >30 days.

Cardiovascular Disease-Related Criteria (see also other cardiovascular exclusion criteria #22)

15. **MI or acute coronary syndrome:** within the 8 weeks prior to screening through to randomization. (Day 1)
16. **Stroke or transient ischemic attack:** within the 8 weeks prior to screening through to randomization. (Day 1)
17. **Heart failure:** Chronic Class IV heart failure, as defined by the New York Heart Association (NYHA) functional classification system
18. **QTcB (Day 1):** QTcB >500 msec or QTcB >530 msec in participants with bundle branch block. There is no QTc exclusion for participants with a predominantly paced rhythm.

Other Disease Related Criteria**19. Liver Disease-Related Criteria:**

- Alanine transaminase (ALT) >2x upper limit of normal (ULN) at screening (Week -4).
- Bilirubin >1.5xULN at screening (Week -4). NOTE: Isolated bilirubin >1.5xULN is acceptable if bilirubin is fractionated and direct bilirubin <35%.
- Current unstable liver or biliary disease per investigator assessment, generally defined by the presence of ascites, encephalopathy, coagulopathy, hypoalbuminaemia, esophageal or gastric varices, persistent jaundice, or cirrhosis. NOTE: Stable chronic liver disease (including asymptomatic gallstones, chronic hepatitis B or C, or Gilbert's syndrome) is acceptable if participant otherwise meets entry criteria.

20. **Malignancy:** History of malignancy within the 2 years prior to screening through to randomization (Day 1), or currently receiving treatment for cancer, or complex kidney cyst (e.g. Bosniak Category II F, III or IV) > 3cm. Note: The only exception is localized squamous cell or basal cell carcinoma of the skin that has been definitively treated ≥ 8 weeks prior to screening.

Other Exclusion

21. **Other Conditions:** Any other condition, clinical or laboratory abnormality, or examination finding that the investigator considers would put the participant at unacceptable risk, which may affect study compliance or prevent understanding of the aims or investigational procedures or possible consequences of the study.

Other cardiovascular exclusion criteria

22. **Current uncontrolled hypertension:** Current uncontrolled hypertension as determined by the investigator

6.3. Lifestyle Restrictions

There are no lifestyle restrictions required for this study. Any restrictions of concomitant medications and non-drug therapies are described in Section 7.6.1.

6.4. Screen Failures

Screen failures are defined as participants who consent to participate in the clinical study but are not subsequently randomized. A minimal set of screen failure information is required to ensure transparent reporting of screen failure participants to meet the Consolidated Standards of Reporting Trials (CONSORT) publishing requirements and to respond to queries from regulatory authorities. Minimal information includes demography, screen failure details, eligibility criteria, and any serious adverse events (SAEs).

Participants that fail screening are eligible to be rescreened up to two additional times as soon as the investigator assesses they may meet study entry criteria. If participants are rescreened, they must sign a new informed consent form. Rescreened participants will also be assigned a new participant number, while maintaining the link to the participant number used for the initial screening.

7. TREATMENTS

Study treatment is defined as daprodustat or matching placebo, intended to be administered to a study participant according to the study protocol. Once daily oral daprodustat starting doses or matching placebo are assigned based on the HemoCue Hgb concentration at randomization (Day 1) (Table 4).

Table 4 Daprodustat Starting Dose

Baseline (Day 1) Hgb (g/dL)	Daprodustat Starting Dose (mg, once daily)
8.5 to <9	4
9 to 10	2

7.1. Treatments Administered

[figure not shown]
Participants randomized on Day 1 to either daprodustat or placebo will receive 3 bottles, and will take one tablet from each bottle at each dose. The study treatments to be administered in this study are described in Table 5.

Table 5 Description of Daprodustat and Matching Placebo Tablets

Study Treatment Name:	Daprodustat (GSK1278863)	Placebo
Dosage formulation:	film-coated tablet	film-coated tablet
Unit dose strength(s)/Dosage level(s):	Unit dose strength: 7mm tablet: 1mg, 2mg, 4mg 9mm tablet: 6mg, 8mg, 10mg Dosage levels: 1, 2, 4, 6, 8, 10, 12, 16 mg	Unit dose strength: Matching 7mm and 9mm tablets Dosage levels: Matching 1, 2, 4, 6, 8, 10, 12, 16 mg
Route of Administration	oral	oral
Dosing instructions:	3 Tablets are to be taken daily with water. Tablets can be taken without regard to food.	3 Tablets are to be taken daily with water. Tablets can be taken without regard to food.
Packaging and Labeling	Study Treatment will be provided in white, opaque high density polyethylene (HDPE) bottles with child-resistant closures. Each bottle will be labeled as required per country requirement.	Study Treatment will be provided in white, opaque high density polyethylene (HDPE) bottles with child-resistant closures. Each bottle will be labeled as required per country requirement.
Manufacturer	GlaxoSmithKline	GlaxoSmithKline

7.2. Dose Modification

The available dose steps of daprodustat and placebo are outlined below. Dose adjustments (increase or decrease by one dose step, maintain, or withheld if ≥ 13 g/dL) will be made programmatically for both the daprodustat arm and the matching placebo arm by the IRT system to increase and maintain hemoglobin within the target range based on the HemoCue Hgb value measured at least every 4 weeks. Those receiving the highest dose of daprodustat, or dose matched placebo, who require a dose increase will maintain the same dose, while those receiving the lowest dose of daprodustat, or matching placebo, that require a dose decrease will receive placebo until such time as when study treatment can be restarted according to [Table 6](#).

Dose adjustment decisions will be based on individual participant HemoCue Hgb response. The decision to proceed to the next dose (either an increase or a decrease) or maintain current dose will be conducted as follows:

Table 6 Study treatment dosing algorithm

HemoCue Hgb (g/dL) at current study visit ¹	HemoCue Hgb change since last study visit ¹	Study Treatment Dose Adjustment ⁶
<8.5 ²	Any change	Repeat Hgb and average values, if confirmed ⁸ ; Increase dose to next higher step AND evaluate for rescue criteria ⁷
8.5 to <10.5	Hgb increase <0.5 g/dL or any Hgb decrease or No change	Increase dose to next higher step
8.5 to <10.5	Increase by ≥ 0.5 and ≤ 2 g/dL	Maintain dose
≥ 10.5 to ≤ 12.5	Any change ≤ 2 g/dL ⁴	Maintain dose
≥ 10.5 to <11.0 at 2 consecutive visits	Decreasing or No change	Increase to the next higher dose step
>12.0 to ≤ 12.5 at 2 consecutive visits	Increasing or No change	Decrease to the next lower dose step
>12.5 to <13	Decreasing	Maintain dose
> 12.5 to <13	Increasing or No change	Decrease to the next lower dose step
≥ 13.0 ³	Any change ⁵	Repeat Hgb and average values ⁸ ; if confirmed, temporarily hold the dose and re-check Hgb at next study visit ¹ ; restart at one dose step lower when Hgb <12.0 g/dL and provided it has been at least 2 weeks from the prior study visit.
Any	>2 g/dL increase over 4 weeks (>1 g/dL increase over 2 weeks ^{2,5})	Repeat Hgb and average values ⁸ ; if confirmed, decrease to the next lower dose step
Any	>2 g/dL decrease over 4 weeks (>1 g/dL decrease over 2 weeks ^{2,5})	Repeat Hgb and average values ⁸ ; if confirmed, increase to the next higher dose step ⁷

1. "Study visit" refers to scheduled visits as outlined in SoA.
2. This rule applies to any scheduled or unscheduled visit, provided it has been at least 2 weeks from the prior study visit.
3. This rule applies to any scheduled or unscheduled visit
4. Any change is defined as an increase, decrease or no change of ≤ 2 g/dL, from prior study visit, when Hgb is ≥ 10.5 or < 12.5 g/dL.
5. This rule applies to Week 2 visits as well.
6. Those receiving the highest dose of study treatment who require a dose increase will maintain the same dose, while those receiving the lowest dose of study treatment that require a dose decrease will have doses withheld.
7. If HemoCue Hgb <8.5 g/dL, then also consider participant for rescue criteria per protocol Section 7.7.2.
8. Repeat HemoCue Hgb at the same study visit to confirm Hgb (using the same sample) and take average.

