| 
 • Assigned dose by visit • Most recent dose prior to Week 24, Week 28 and end of study treatment • Maximum achieved dose • Number (%) of participants with 0, 1, 2, or >2 dose adjustments during the treatment period • Mean and median number of dose adjustments during the treatment period • Time dose held for Hgb ≥ 13 g/dL during the treatment period |
| Planned Exploratory Displays |
| 
 • The assigned dose by visit will be summarized using mean, standard deviation, minimum, P25, median, P75, and maximum. • The most recent dose prior to Week 28 and end of treatment will be summarized by the number and percentage of participants at each dose level. • The maximum achieved dose will be summarized using mean, standard deviation, minimum, P25, median, P75, and maximum. • The number and percentage of participants with 0, 1, 2, or >2 dose adjustments will be summarized by treatment group during the treatment period. This summary will be produced twice – the first time counting all dose adjustments, including adjustments related to periods of dose holds (i.e., no study treatment is given), the second time excluding dose adjustments related to periods of dose hold. • The time (in days) that study treatment was withheld for Hgb values ≥ 13 g/dL per participant will be summarized using mean, standard deviation, minimum, P25, median, P75, and maximum during the treatment period. |

Blood Pressure

| Endpoint / Variables |
|--|
| 
 • N (%) of subjects who had no change, an increase or a decrease in the number of BP medications from baseline to week 28 or final visit for non-completers |
| Planned Exploratory Displays |
| 
 • Summary table listing the N (%) of subjects in each treatment group who have no change, an increase or a decrease in the number of BP medications from baseline to week 28 or final visit for non-completers. Summary to include: 
 ○ For subjects who have no change in the number and class of blood pressure medications taken between baseline and Week 28. ○ For subjects who have the same number of blood pressure medications taken at baseline and Week 28, but a change in the class ○ For subjects who have an increase in the number of blood pressure medications taken between baseline and Week 28 ○ For subjects who have a decrease in the number of blood pressure medications taken |

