| 
 • Date of last actual dose of randomized study treatment from the IP Discontinuation eCRF form. 
 ○ The dose steps used by the dosing algorithm described in the protocol include a dose hold or a zero dose. If participants are assigned by the algorithm to a zero dose, they do not receive randomized treatment for that period. Hence, it would be possible for a participant to complete the study, while still following the dosing algorithm, but not actually taking any actual randomized treatment. The last non-zero dose date then captures the latest date in the study that a participant physically took a dose of randomized treatment. • The eCRF allows for the possibility of partial or missing dates to be recorded for the last actual dose of randomized study treatment on the IP Discontinuation form (i.e., missing day, or day and month, or day and month and year). In such a case, or in case of a missing IP Discontinuation form, the following conventions will be applied in order to impute a last non-zero dose date: 
 ○ Missing day: 
 ▪ The last day of the month will be used, unless the treatment stop date also occurs in the same month; in this case, the treatment stop date will be used. ○ Missing day and month; 
 ▪ ‘31’ will be used for the day and ‘Dec’ will be used for the month, unless the treatment stop date also occurs in the same year; in this case the treatment stop date will be used. ○ Missing day, month, and year: 
 ▪ Treatment stop date will be used only for participants who have a non-missing treatment start date. |

CONFIDENTIAL

205270

| |
|---|
| General |
| Treatment Stop Date |
| 
 Calculated as the latest randomized treatment dose stop date. The eCRF does not allow for the possibility of missing or partial dates to be recorded for the dose stop date on the study treatment form |
| End of Treatment Value |

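### Monthly iron windows end on different dates in the two arms, and the documents disagree on what is dispensed at zero dose

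*Protocol*

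**What the plan says.** **Iron window.** SAP 10.6.3 (average monthly IV iron) cuts the window short when treatment ends before Week 28. It takes the last non-zero dose date as the end for daprodustat and the treatment end date for placebo. The oral iron averages, from randomization to Week 28 and from Week 24 to Week 28, are told to follow the IV calculation. SAP 7.4.2 (Iron Parameters) divides total iron on randomized treatment by days on randomized treatment/30.4375, with no difference between arms.

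**The date.** SAP 10.6.1 defines the last non-zero dose date as "Date of last actual dose of randomized study treatment from the IP Discontinuation eCRF form". It adds that when the algorithm assigns a zero dose to participants, "they do not receive randomized treatment for that period". The date closes the on-treatment window for blood pressure, laboratory and vital-sign data (SAP 10.4.1.2) and the treatment-emergent window for adverse events (10.4.2). It also fixes the end-of-treatment value for those parameters (10.6.1).

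**Delivery at zero dose.** In the Protocol 7.2 text, participants on the lowest dose "that require a dose decrease will receive placebo until such time as when study treatment can be restarted". Table 6 footnote 6 says "those receiving the lowest dose of study treatment that require a dose decrease will have doses withheld". SAP 7.4.2 counts dose adjustments "including adjustments related to periods of dose holds (i.e., no study treatment is given"). Protocol 7 defines the term broadly: "Study treatment is defined as daprodustat or matching placebo". Protocol 5.1 has the IRT change doses "in order to ensure that investigators and participants stay blinded to the study treatment and the dose adjustments".

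**Restart.** The only explicit restart instruction in Table 6 is in the Hgb ≥13 row: "restart at one dose step lower when Hgb <12.0 g/dL".

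**The concern.** A randomized comparison should measure both arms over windows defined in the same way. Here the iron window can be cut short in the daprodustat arm only, so two participants with the same dosing and iron history can get different monthly averages because of their arm. The SAP also disagrees with itself, since 7.4.2 makes no such distinction.

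The date that cuts the window has a weakness of its own. If matching tablets continue at zero dose, a blinded site may record the last tablet as the last dose. If tablets stop, the recorded date falls earlier. The protocol text and its footnote point in different directions, and the SAP reads as no tablets at all. The same date decides whether late blood pressure and laboratory readings count as on-treatment. It does so for participants whose Hgb was high or rising fast, and worsening of hypertension is an adverse event of special interest (Protocol 9.3.7).

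**Working it through.** **1. Monthly iron, same history in each arm.** The formula in SAP 7.4.2 is total mg / (days in window / 30.4375). Assume one 1000 mg IV dose and zero dose from Week h to Week 28. The full window is 28 × 7 = 196 days; cut at the last non-zero dose it is 7h days.

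| Zero dose from | Cut window (days) | Placebo, full window | Daprodustat, iron given earlier | Ratio | Daprodustat, iron given during zero dose |
|---|---|---|---|---|---|
| Week 24 | 168 | 155.3 mg/month | 181.2 | 196/168 = 1.17 | 0 |
| Week 20 | 140 | 155.3 | 217.4 | 196/140 = 1.40 | 0 |
| Week 16 | 112 | 155.3 | 271.8 | 196/112 = 1.75 | 0 |

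The direction depends on when iron was given. A constant daily dose d gives (d × 168)/(168/30.4375) = 30.4375 × d, the same as over 196 days. The distortion therefore arises when iron use changes over time. With one end date for both arms (treatment end, day 196), the result is 155.3 mg/month in either arm.

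**2. Effect on the arm mean.** The documents give no count of participants at zero dose in the final period. An illustrative simulation applied Table 6 at the protocol visits, 20,000 per arm. The starting dose was set to raise Hgb by about 1 g/dL (Protocol 5.5). Dose-response shape, between-participant spread, untreated drift and visit noise were all assumed. With restart below 12.0 g/dL, the share at zero dose in the final period was 0.2%, 2.3% and 6.5% of daprodustat in low, middle and high scenarios, against 0.0%, 0.6% and 3.4% of placebo. If the lowest step is left only through the increase rows, the daprodustat shares are 0.6%, 4.1% and 9.9%.

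If affected participants use average amounts of iron, all of it before zero dose began, the daprodustat mean shifts by share × (ratio − 1):

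- lowest: 0.2% × 16.7% = 0.03%
- middle, from Week 20: 2.3% × 40% = 0.9%
- extreme: 9.9% × 75% = 7.4%

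**3. The delivery sentences side by side.** The 7.2 text dispenses placebo and footnote 6 withholds doses. The two agree if the active dose is withheld and matching tablets continue, but neither document says so. The SAP says no study treatment is given during holds. Because study treatment includes matching placebo, that wording reads as no tablets.

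**4. What depends on the date.** Take zero dose from Week 16, 20 or 24 to Week 28. If tablets stop, the last dose falls near day 112, 140 or 168. If placebo is dispensed and recorded as the last dose, it falls near day 196. The difference is 84, 56 or 28 days. Blood pressure is scheduled at Weeks 2, 4, 16 and 28 and chemistry at Weeks 4, 16 and 28 (Protocol Table 1), so Week 28 is the one scheduled reading at stake. It enters or leaves the on-treatment blood pressure model (SAP 7.3.2.1), the exacerbation count (10.6.3) and the worst-case on-treatment tables (10.10.8).

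**5. What does not depend on it.** The primary Hgb analysis uses on- and off-treatment values. On-treatment status for Hgb and patient-reported outcomes, including SF-36, uses the treatment stop date (10.4.1.1). By-visit vital-sign and laboratory tables are post-randomization, on and off treatment.

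**The case against.** The strongest reply is that the documents already hold a workable reading. The 7.2 text dispenses placebo, 5.1 requires blinded dose changes, and participants take tablets from three bottles at every dose (7.1). SAP 10.6.2 even shows a 0 mg bottle contributing nothing to the dose. The SAP phrases about holds are analysis conventions, not dispensing instructions, and the IRT assigns doses, so sites do not choose between sentences. This stands as the likely intention. It does not remove the mismatch in the text, and it makes the date more fragile: the more surely tablets continue, the more the last tablet may be recorded as the last dose. That link is itself uncertain, because the IP Discontinuation form is not in the documents.

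A reader might infer that the iron rule distorts the comparison on any reading. It does not. If placebo is dispensed and the last tablet is recorded, the last non-zero dose date equals the treatment end date and the difference between arms disappears. The rule is wrong under the SAP's own meaning of zero dose. The 17% also relies on the 7.4.2 denominator. A formula printed later in 10.6.3, labelled as baseline, uses a fixed 16 × 7 days.

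On adverse events, SAP 10.4.2 keeps those arising during treatment interruptions as treatment-emergent. It does not say whether a final zero-dose period, with no resumption, is an interruption. Events after the cut-off still appear in the follow-up tables.

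**Conclusion.** The point holds and is minor. As written, the end of the monthly iron window differs by arm. Under the SAP's meaning of zero dose, earlier iron gives a monthly average 17% higher on daprodustat for a participant at zero dose from Week 24, and later iron is lost. Few participants are likely to be affected, and the endpoint is exploratory with no planned test (SAP 7.4). The delivery conflict may change on-treatment status and the treatment-emergent cut-off for a final zero-dose period. Its size is unknown: the simulated shares rest mostly on assumed inputs and show only that the event can occur. Blood pressure comparisons carry no multiplicity control (SAP 5.5).

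Three stronger conclusions are not supported:

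- **No way back from zero.** One dose step lower than 1 mg is not a listed level. However, SAP 10.6.1 counts zero among the algorithm's steps, so the increase rows of Table 6 return a participant to 1 mg. Only the threshold is unclear: below 12.0 g/dL as after a hold, or the lower values in the increase rows.
- **Unblinding of the arm.** The algorithm runs in both arms, so stopping tablets would reveal a dose adjustment, not the treatment assigned.
- **Biased blood pressure results.** Nothing in the documents allows a bias to be estimated.

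**What to change.** - **(a) Iron, SAP 10.6.3.** Use one end-date rule in both arms for monthly IV and oral iron, including the Week 24 to 28 oral average. The treatment end date is simplest and does not shorten the window more often in the arm where Hgb rises more.
- **(b) Delivery, Protocol 7.2.** Change footnote 6 to match the text: at zero dose, matching placebo tablets continue in both arms. Align SAP 7.4.2 and 10.6.1 by saying that no non-zero dose level is assigned, rather than that no treatment is given.
- **(c) Date, SAP 10.6.1.** Derive the last non-zero dose date from the IRT-assigned dose level, active or matching, capped at the last tablet date, identically in both arms.
- **(d) Restart.** State which Hgb threshold governs return from zero to 1 mg. The threshold, and the restart after a hold at ≥13 g/dL from 1 mg, should be left to the sponsor's clinical team. Returning to 1 mg after such a hold would depart from the step-down that Table 6 requires and is a clinical trade-off.

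The cost is wording, some programming, and placebo bottles for zero-dose periods. Matching tablets and IRT zero-dose records already exist. The small burden is that participants take inactive tablets while at zero dose. Items (a) and (c) can be made in the SAP alone if the protocol can no longer change; (b) then becomes a statement of what was actually dispensed.
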